## **Study Protocol and Statistical Analyses Plan**

Recent studies have shown that C natriuretic peptide (CNP) is produced from granulosa cells, increasing cumulative guanosine monophosphate (cGMP) production by affecting cumulus cells through natriuretic peptide receptors. It is suggested that produced cGMP maintains the transport of oocytes via the gap junctions and leads to a continuous increase in cyclic adenosine monophosphate (cAMP) levels in the oocyte. An important role of increased internal cAMP levels in the oocyte is shown to suppress meiotic progression.

Deoxyribonucleic acid studies in animals have shown that expression of the natriuretic peptide precursor increases during the periovulatory period and shows that this increase decreases rapidly after luteinizing hormone (LH) / human chorionic gonadotropin (hCG) stimulation. Human studies have shown that after ovulation induction, the CNP level in follicular fluid decreases following ovulatory dose of hCG. Polycystic ovary syndrome (PCOS) is the most common endocrine disease in the reproductive period, characterized by hyperandrogenism, oligo-anovulation, and polycystic ovarian morphology on ultrasonography. Recently, a study on PCOS-like mouse model investigated the effect of CNP/ natriuretic peptide receptor 2 (NPR2) on oocyte maturation and anovulation. They increased the expression of CNP/NPR2 with hyperandrogenism and showed meiotic arrest and anovulation in the subject oocytes. Conversely, they showed that reducing CNP/NPR2 production led to partial recovery of ovulation. CNP serum level is thought to show differences between healthy women and women with polycystic ovary syndrome.

In the light of these data, we conclude that in PCOS, which is known to be associated with hyperandrogenism and anovulation, serum levels of CNP, which is also associated with these components, may be elevated. In this study, it was aimed to determine serum CNP levels in PCOS patients, their relationship with serum androgens, and comparison with the healthy group.

In this prospective study, a total of 66 patients admitted to the Department of Obstetrics and Gynecology of the Near East University Hospital were included. PCOS group consisted of 36 women and control group included 30 healthy women with regular menstruation aged between 18-40 years old. PCOS diagnosis was made according to Rotterdam criteria. PCOS diagnosis was made in the presence of two or three of these findings; oligo/anovulation, polycystic ovaries on ultrasonography and clinical or biochemical manifestations of hyperandrogenism.

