# Comparison of Serum C Type Natriuretic Peptide Levels Between Polycystic Ovary Syndrome Patients and Healthy Women

NCT04006171

Date:01.07.2021

Age, body mass index (BMI), serum levels of LH, follicle stimulating hormone (FSH), estradiol, thyroid stimulating hormone (TSH), prolactin (PRL), androstenedione, dehydroepiandrosterone sulfate (DHEAS), total testosterone, free testosterone, sex hormone binding globulin (SHBG), total cholesterol (TC), triglyceride (TG), high density lipoprotein (HDL), low density lipoprotein (LDL), glucose and insulin levels were measured. For insulin sensitivity, homeostatic model of insulin resistance (HOMA-IR) was used. Free androgen index (FAI) was calculated for all participants.

Exclusion criteria were as follows: age over 40 years, current pregnancy, hyperprolactinemia, thyroid disease, congenital adrenal hyperplasia, a history of ovarian surgery or any other systemic disease or drugs that could influence hypothalamic pituitary ovarian axis, androgen production, insulin and or/glycemic metabolism, patients with cardiac or renal disease and therefore drug use, patients who received any hormone therapy including contraceptives up to 6 months before study.

Morning fasting venous blood samples were taken from the patients on the 2nd or 3rd day of the menstruation for all participants. All blood samples were centrifuged on the day of collection and separated serum samples and were kept at -80 degrees celcius until the day of CNP test. Serum CNP levels of the patients were analyzed by an enzyme-linked immunosorbent (ELISA) assay for human CNP in accordance with the manufacturer's instructions (SEA721Hu, ELISA Kit for Human CNP, Wuhan USCN Business Co., Ltd., Cloud-Clone Corp., CCC, USA).

Data were analyzed using Statistical Package for Social Sciences software (SPSS v15, SPSS Inc, Chicago, IL, USA). Data were presented as mean±standard deviation or median and interquartile range. Independent t-test was used to compare the parameters with normal distribution. Parameters that don't fulfill the parametric test assumptions were compared using Mann-Whitney U test. Correlation of CNP with other parameters was analyzed using Spearman's rank correlation test. Receiver operating characteristic (ROC) curve was used to evaluate diagnostic sensitivity and specificity of CNP for PCOS. P values less than 0.05 were regarded as statistically significant.

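### Does the plan need a rule showing that the controls were free of PCOS, given that regular menstruation excludes only one of the three Rotterdam findings?

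*Combined protocol and SAP*

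**What the plan says.** The section headed Study Protocol and Statistical Analyses Plan describes "a total of 66 patients admitted to the Department of Obstetrics and Gynecology". Of these, the "PCOS group consisted of 36 women" and the "control group included 30 healthy women with regular menstruation aged between 18-40 years old". PCOS is diagnosed by the Rotterdam rule, "in the presence of two or three of these findings; oligo/anovulation, polycystic ovaries on ultrasonography and clinical or biochemical manifestations of hyperandrogenism". The background in the same section gives the contrast under study: "CNP serum level is thought to show differences between healthy women and women with polycystic ovary syndrome".

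The section titled with the study name lists the measurements, which include androstenedione, DHEAS, total and free testosterone and SHBG. It adds that "Free androgen index (FAI) was calculated for all participants", and that fasting blood was drawn from everyone on cycle day 2 or 3. The exclusions, which are not separated by group, cover thyroid disease, hyperprolactinaemia, congenital adrenal hyperplasia, recent hormone therapy and "any other systemic disease or drugs that could influence hypothalamic pituitary ovarian axis, androgen production, insulin and or/glycemic metabolism". Among the analyses, a ROC "curve was used to evaluate diagnostic sensitivity and specificity of CNP for PCOS".

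Neither section states that controls had an ultrasound or a clinical assessment for hyperandrogenism, and neither gives an androgen limit for entry as a control.

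**The concern.** Cases are defined by two findings out of three, while the one specific criterion for controls addresses at most one finding, oligo/anovulation. By the plan's own rule, a woman who menstruates regularly but has polycystic ovaries and hyperandrogenism has PCOS, and she could still enter as a control. The controls were also recruited through an obstetrics and gynaecology department, so one may ask what healthy was taken to mean.

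Two results depend on correct control status. A woman with undetected PCOS among the 30 controls would shrink the group difference in CNP. She would also count as a false positive in the ROC when her CNP is high, which lowers the apparent specificity. The woman most easily missed is hyperandrogenic, and the study's hypothesis links CNP to hyperandrogenism, so the error would fall on the question being asked.

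**Working it through.** **What the text covers for controls**

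| Rotterdam finding | What the document gives for controls |
|---|---|
| Oligo/anovulation | Regular menstruation required |
| Polycystic ovaries on ultrasound | No assessment described |
| Hyperandrogenism, biochemical | Androgens measured and FAI calculated for all participants; no limit or eligibility use stated |
| Hyperandrogenism, clinical | No assessment described |

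The gap is therefore narrower than two findings wholly unchecked: the biochemical data exist for every control. The exclusion list does not settle the matter. *Any other systemic disease* may mean, for controls, any disorder of androgen production including PCOS, but the list names no test.

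**Inputs.** From the document: 36 cases, 30 controls (36 + 30 = 66, the stated total) and a 0.05 significance level, taken as two-sided. The document gives no effect size, CNP cut-off or rate of missed PCOS, so these are assumed: a true difference of 0.70 SD (about what 36 versus 30 detects with 80% power), normal data, and a cut-off with 80% specificity. Let k be the number of missed cases among controls, f = k/30, and s the share of the PCOS shift that such a woman carries (0.5 or 1).

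**Formulas**

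- Diluted difference: 0.70 × (1 − f·s).
- Power: noncentral t, 64 degrees of freedom, standard error √(1/36 + 1/30) = 0.247 SD.
- Specificity: (1 − f) × 0.80 + f × Φ(0.842 − 0.70·s).
- AUC: (1 − f) × Φ(0.70/√2) + f × Φ(0.70·(1 − s)/√2).

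**Results** (first figure s = 0.5, second s = 1)

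| k | Difference (SD) | Power | Specificity | AUC |
|---|---|---|---|---|
| 0 | 0.700 | 0.796 | 0.800 | 0.690 |
| 1 | 0.688 / 0.677 | 0.783 / 0.769 | 0.796 / 0.792 | 0.687 / 0.683 |
| 3 | 0.665 / 0.630 | 0.755 / 0.709 | 0.789 / 0.776 | 0.680 / 0.671 |

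**Against sampling error**

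- Specificity of 80% from 30 controls has standard error √(0.8 × 0.2/30) = 0.073. The largest shift in the table is 0.800 − 0.776 = 0.024, about a third of that.
- An AUC of 0.69 with 36 and 30 women has a Hanley-McNeil standard error of about 0.065. The largest shift is 0.690 − 0.671 = 0.019.
- The largest loss in the mean difference is 0.700 − 0.630 = 0.070 SD, against a standard error of 0.247 SD.

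**A more extreme case.** With 6 of 30 controls affected (20%) and s = 1, specificity is 0.8 × 0.80 + 0.2 × 0.556 = 0.751 and AUC is 0.8 × 0.690 + 0.2 × 0.5 = 0.652. Both shifts (0.049 and 0.038) remain within one standard error. Power, by the normal approximation from a starting value of 80%, would be about 61%.

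**The case for a change.** The best argument for a change is that specificity describes women known not to have the condition, so a reader should be told what reference standard the controls met. One or two sentences would do it. The word *healthy* shows intent but not verification, and androgen values alone cannot decide a two-of-three rule. A null or weak CNP result would be harder to interpret if control status were uncertain, and under the heavier assumptions the loss of power is not trivial: 9 points with three missed cases that carry the full shift.

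Much of this stands. The document does not describe the check, and the study report should. It does not follow that the ROC is uninterpretable, since the illustrated distortion is small beside the sampling error of 30 controls. Describing the participants as patients adds little, because the document uses that word interchangeably with participants. The power loss could not be recovered by a change now either: the document is written in the past tense with both groups already formed, and an analysis rule cannot supply an ultrasound that was not done.

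**Conclusion.** No change to the plan is needed. The plan leaves out a detail that the investigators can be expected to supply sensibly: controls are meant to be women without PCOS, the background and the study title both set them against PCOS, and biochemical androgen data are available for all of them. When the study is reported, it is ordinary practice to say how control status was established, or to give reliance on menstrual history as a limitation.

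The size of any effect is unknown and may be zero. If one to three of the 30 controls were missed cases, specificity would fall by 0.4 to 2.4 points, the AUC by about 0.003 to 0.019, and power by about 1 to 9 points. These figures rest on the assumed 0.70 SD difference, 80% specificity, normal data, and a missed case carrying half or all of the PCOS shift. With a shift in the same direction as in the cases, the error is conservative: it can shrink a real CNP difference but cannot create one. The conclusion would need another look only if existing records showed that a control met two of the three findings.

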# Comparison of Serum C Type Natriuretic Peptide Levels Between Polycystic Ovary Syndrome Patients and Healthy Women

NCT04006171

Date:01.07.2021

Age, body mass index (BMI), serum levels of LH, follicle stimulating hormone (FSH), estradiol, thyroid stimulating hormone (TSH), prolactin (PRL), androstenedione, dehydroepiandrosterone sulfate (DHEAS), total testosterone, free testosterone, sex hormone binding globulin (SHBG), total cholesterol (TC), triglyceride (TG), high density lipoprotein (HDL), low density lipoprotein (LDL), glucose and insulin levels were measured. For insulin sensitivity, homeostatic model of insulin resistance (HOMA-IR) was used. Free androgen index (FAI) was calculated for all participants.

Exclusion criteria were as follows: age over 40 years, current pregnancy, hyperprolactinemia, thyroid disease, congenital adrenal hyperplasia, a history of ovarian surgery or any other systemic disease or drugs that could influence hypothalamic pituitary ovarian axis, androgen production, insulin and or/glycemic metabolism, patients with cardiac or renal disease and therefore drug use, patients who received any hormone therapy including contraceptives up to 6 months before study.

Morning fasting venous blood samples were taken from the patients on the 2nd or 3rd day of the menstruation for all participants. All blood samples were centrifuged on the day of collection and separated serum samples and were kept at -80 degrees celcius until the day of CNP test. Serum CNP levels of the patients were analyzed by an enzyme-linked immunosorbent (ELISA) assay for human CNP in accordance with the manufacturer's instructions (SEA721Hu, ELISA Kit for Human CNP, Wuhan USCN Business Co., Ltd., Cloud-Clone Corp., CCC, USA).

Data were analyzed using Statistical Package for Social Sciences software (SPSS v15, SPSS Inc, Chicago, IL, USA). Data were presented as mean±standard deviation or median and interquartile range. Independent t-test was used to compare the parameters with normal distribution. Parameters that don't fulfill the parametric test assumptions were compared using Mann-Whitney U test. Correlation of CNP with other parameters was analyzed using Spearman's rank correlation test. Receiver operating characteristic (ROC) curve was used to evaluate diagnostic sensitivity and specificity of CNP for PCOS. P values less than 0.05 were regarded as statistically significant.

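### Age and BMI are measured, but no planned step carries either into the PCOS versus healthy CNP comparison, which stays an unadjusted two-sample test

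*Combined protocol and SAP*

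**What the plan says.** The aim, given in the section headed *Study Protocol and Statistical Analyses Plan*, is that "it was aimed to determine serum CNP levels in PCOS patients, their relationship with serum androgens, and comparison with the healthy group". The same section describes the sample: "PCOS group consisted of 36 women and control group included 30 healthy women with regular menstruation aged between 18-40 years old". Matching is not mentioned. The exclusion criteria repeat the upper age limit and set no limit on BMI.

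The measurements paragraph, in the section under the study title, begins "Age, body mass index (BMI), serum levels of LH, follicle stimulating hormone (FSH), estradiol", so both covariates are available for every participant.

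The statistical paragraph at the end of that section names four tools:

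- For group differences in normally distributed variables: "Independent t-test was used to compare the parameters with normal distribution".
- Variables that fail the parametric assumptions "were compared using Mann-Whitney U test".
- "Correlation of CNP with other parameters was analyzed using" Spearman's rank method. Whether this is done within groups or on the pooled sample is not stated.
- A ROC curve for CNP as a marker of PCOS.

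No regression, analysis of covariance, stratification, partial correlation or covariate-adjusted ROC analysis is named.

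**The concern.** The groups are defined by diagnosis, so nothing in the design makes them alike in BMI, and age is restrained only by the 18-40 range. The background section motivates the CNP comparison by PCOS biology (hyperandrogenism, anovulation, meiotic arrest), so readers will take a CNP difference as something related to PCOS.

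The crude difference is a legitimate quantity, and it also underlies the ROC analysis. But it combines any PCOS-related difference with any difference that comes from age or BMI. An imbalance could appear as a PCOS difference or hide one. The plan can reveal both ingredients of the problem (a group difference in BMI, and a correlation of BMI with CNP) and then has no step that uses them.

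**Working it through.** The documents give no power calculation, effect size or standard deviation, so there is no planned figure to reproduce beyond 36 + 30 = 66, which agrees.

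**Inputs from the documents.** Group sizes 36 and 30; significance level 0.05, taken as two-sided because sidedness is not stated.

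**Assumed inputs.** D is the difference in mean BMI between groups, in within-group SDs. r is the within-group correlation of BMI with CNP. The documents give neither, so ranges are shown. CNP is scaled to a within-group SD of 1.

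**Step 1: significant results when there is no difference at equal BMI.** The crude CNP difference then has expectation r × D. Its standard error is √(1/36 + 1/30) = 0.247, so the noncentrality is r × D × √(36 × 30/66) = r × D × 4.045, with 64 degrees of freedom. For example, D = 0.5 and r = 0.5 give 0.25 × 4.045 = 1.01 and a rejection rate of 16.9%.

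| D | r = 0.2 | r = 0.3 | r = 0.5 |
|---|---|---|---|
| 0 | 5.0% | 5.0% | 5.0% |
| 0.25 | 5.5% | 6.0% | 7.9% |
| 0.5 | 6.8% | 9.2% | 16.9% |
| 0.8 | 9.8% | 16.0% | 35.7% |
| 1.0 | 12.5% | 22.3% | 51.3% |

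The Mann-Whitney test behaves much the same in simulation: 9.0% and 15.7% at D = 0.5 (r = 0.3 and 0.5), and 21.5% and 48.6% at D = 1.0. The formula is identical for an age imbalance of the same size.

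For scale, this sample has 80% power for a difference of (1.96 + 0.84) × 0.247 ≈ 0.69 SD. A bias of 0.15 to 0.50 SD (D = 0.5, r = 0.3 to D = 1.0, r = 0.5) is 22% to 72% of that.

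**Step 2: masking.** Take a true 0.7 SD difference at equal BMI and bias in the opposite direction. The crude difference is 0.7 − |r| × D.

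| D | \|r\| | Crude difference | Power |
|---|---|---|---|
| 0 | any | 0.70 | 80% |
| 0.5 | 0.3 | 0.55 | 59% |
| 1.0 | 0.3 | 0.40 | 36% |
| 1.0 | 0.5 | 0.20 | 12.5% |

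**Step 3: would checking BMI for balance first be enough?** The noncentrality of the t-test on BMI is D × 4.045. Its power is 17%, 51%, 89% and 98% at D = 0.25, 0.5, 0.8 and 1.0. A non-significant BMI comparison is therefore weak reassurance at a moderate imbalance.

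**Step 4: the price of adjusting.** Collinearity between group and BMI inflates the standard error by √(1 + (36/66)(30/66) × D²) = √(1 + 0.248 × D²), which is 1.03, 1.08 and 1.12 at D = 0.5, 0.8 and 1.0. Lower residual variance gives part of this back: the simulated net ratio runs from 1.03 (r = 0.2) to 0.91 (r = 0.5) at D = 0.5, and from 1.12 to 0.99 at D = 1.0. Simulated power of the model with group, BMI and age for a true 0.7 SD difference (r = 0.3) is 82%, 79%, 76% and 73% at D = 0, 0.5, 0.8 and 1.0; repeat simulations agree to about one percentage point. Under the null the adjusted test rejects in about 5% of runs, but this holds by construction, since the simulations make the covariates pure linear confounders.

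**The case against.** The strongest reply is that the stated aims are descriptive and diagnostic, and that the planned tests answer them. The t-test's null hypothesis is equal mean CNP in the two groups. If r × D is not zero, the means do differ and rejection is correct. The percentages in Step 1 are false positives only for a reader who wants the difference at equal BMI, and Step 2 is a loss of power only in that sense. BMI may also be partly a consequence of PCOS, in which case adjustment removes part of the PCOS difference rather than correcting a bias. D, r and their signs are all assumed, and the largest figures need a 1 SD imbalance together with r = 0.5. Age is partly controlled by the 18-40 range. The exclusions for systemic disease, interfering drugs and recent hormone therapy, with fasting early-cycle sampling, narrow other differences. Finally, a pooled Spearman coefficient need not equal the within-group r used above.

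Most of this stands as qualification. The unadjusted result should remain, the rates must be read as conditional on the equal-BMI question, and the gap is larger for BMI than for age. None of it supplies the missing estimate. The consequence-of-disease argument does not apply to age, and for BMI it is a reason to report both estimates and say what each means.

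**Conclusion.** The point holds. The plan measures age and BMI but contains no analysis that separates a PCOS difference in CNP from an age or BMI difference. This does not invalidate the descriptive comparison; it limits what can be concluded from it.

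The size cannot be known from the documents: there is no distortion if D or r is zero, and it could dominate the result if both are large. The calculations rest on the assumed D and r, unit within-group variance, normality and linear covariate effects. The absence of any adjustment is certain from the text. The improvement is cheap and should be made.

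**What to change.** - Add a linear model of log-CNP on group, age and BMI. Report the adjusted ratio of geometric means, PCOS versus healthy, with its 95% confidence interval, beside the unadjusted comparison.
- If log-CNP is still clearly skewed, use robust or bootstrap intervals so that the ratio stays available.
- State that the unadjusted result is the total difference between the groups, that the adjusted result is the difference at equal age and BMI, and that BMI may be partly a consequence of PCOS.
- Base any claim of a BMI-independent link on the adjusted estimate and its interval. Loss of significance after adjustment is not proof of confounding, given the power loss in Step 4.
- The statistical paragraph is written in the past tense. If the data have already been analysed, say that the adjusted model was added afterwards.

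The cost is one paragraph and one regression on data already collected, two degrees of freedom, and the modest loss of precision shown in Step 4.

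### The CNP-androgen aim is answered only by two-variable Spearman correlations, so a CNP link with body weight can be reported as an androgen link, and a CNP-SHBG link as a CNP-FAI link

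*Combined protocol and SAP*

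**What the plan says.** The closing sentence of the background (combined protocol and SAP, under Study Protocol and Statistical Analyses Plan) gives the aim: "it was aimed to determine serum CNP levels in PCOS patients, their relationship with serum androgens, and comparison with the healthy group". The groups are 36 women with PCOS and 30 controls.

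The measurements paragraph, under the study-title heading, lists BMI, age, SHBG, insulin and several androgens, and adds "Free androgen index (FAI) was calculated for all participants". It gives no formula for FAI.

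The statistical paragraph under the same heading covers associations in one sentence: "Correlation of CNP with other parameters was analyzed using Spearman's rank correlation test". It then says "P values less than 0.05 were regarded as statistically significant". No partial correlation, regression or stratified analysis is named. The eligibility text sets no BMI limit, and no matching on BMI is described. The plan does not say whether the correlations use the PCOS group alone or all 66 women.

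**The concern.** A two-variable rank correlation cannot separate an androgen from something that varies with it. BMI and SHBG enter the plan only as further variables that may be correlated with CNP one at a time. They are not held constant when CNP is set against an androgen.

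There are two routes to a misleading result:

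- **Body weight.** If CNP and an androgen both vary with BMI, they correlate with each other without any direct connection. Analysing PCOS women alone does not help, because lean and obese women with PCOS can differ in CNP and androgens together.
- **SHBG, for FAI only.** If FAI is testosterone over SHBG, it carries SHBG inside it. A CNP-SHBG correlation then produces a CNP-FAI correlation even when CNP and testosterone are unrelated.

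The background argues from hyperandrogenism to raised CNP, so a significant correlation invites an androgen-specific reading. The planned analysis cannot support or refute that reading.

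**Working it through.** The plan states no correlation, power or sample-size figure, so there is nothing to reproduce. The check asks how often P<0.05 would arise with no direct CNP-androgen link.

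**From the documents:** n = 36 (PCOS) or 66 (all women); significance level 0.05.

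**Assumed:** two-sided tests; normal data before ranking; all correlations, shown over a range because the documents give none; FAI = testosterone / SHBG.

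**Threshold.** |rho| needed = t / √(n − 2 + t²), where t is the 97.5% point on n − 2 degrees of freedom. This gives about 0.33 at n = 36 and 0.24 at n = 66.

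**BMI route.** Let BMI correlate a with CNP and b with the androgen, with CNP and the androgen independent given BMI. The induced correlation is a × b. The partial correlation is

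(r_CA − r_CB·r_AB) / √[(1 − r_CB²)(1 − r_AB²)],

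whose numerator here is ab − ab = 0. It is tested on n − 3 degrees of freedom. Simulation with 40,000 replicates per setting:

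| a = b | induced r | plain, n=36 | partial, n=36 | plain, n=66 | partial, n=66 |
|---|---|---|---|---|---|
| 0.3 | 0.09 | 8.0% | 5.1% | 10.3% | 4.8% |
| 0.4 | 0.16 | 14.3% | 5.0% | 23.1% | 5.1% |
| 0.5 | 0.25 | 28.4% | 5.5% | 48.6% | 5.1% |
| 0.6 | 0.36 | 53.9% | 5.3% | 81.2% | 5.4% |

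A separate run of 20,000 replicates at n = 36 gave 7.8%, 14.3%, 28.7% and 54.0%; hence the rounded 8, 14, 29 and 54%. If CNP is unrelated to BMI, the plain test at n = 36 stays at 5.1%.

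**SHBG route.** Take log FAI = log testosterone − log SHBG, with CNP related to SHBG only (correlation −s) and testosterone independent of both. The induced CNP-FAI correlation is s × SD_SHBG / √(SD_T² + SD_SHBG²) on the log scale. With log-SDs of 0.4-0.5 for testosterone and 0.5-0.6 for SHBG, the multiplier runs from 0.5/√(0.25 + 0.25) = 0.71 to 0.6/√(0.16 + 0.36) = 0.83. At n = 36:

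| CNP-SHBG | induced CNP-FAI r | CNP-FAI P<0.05 | CNP-total testosterone P<0.05 |
|---|---|---|---|
| −0.3 | 0.21-0.25 | 22-29% | 5% |
| −0.4 | 0.28-0.33 | 35-47% | 5% |
| −0.5 | 0.35-0.42 | 52-67% | 5% |

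At n = 66 with equal SDs the CNP-FAI figures are 36.9%, 59.1% and 79.8%.

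**Pooling.** If the 36 and 30 women are combined, and both CNP and the androgen are shifted by the same amount in PCOS with no link within either group, P<0.05 occurs in 7.2%, 19.8% and 37.1% of studies at shifts of 0.5, 0.8 and 1.0 SD. This is a separate reason to state the analysis set.

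**Price of adjusting.** With a true direct link of r = 0.45 and BMI unrelated, power at n = 36 falls from 76% to 75% when BMI is held constant.

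**The case against.** The strongest reply is that the aim asks for a relationship and a plain correlation describes one. In the BMI settings CNP and the androgen really are associated, so a significant result is a correct detection. A reader might take the percentages above as false-positive rates of the planned test. They are not: they become misleading only if the result is read as androgen-specific, and the plan contains no rule that says to read it that way. This stands.

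Two further points also stand:

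- The correlations are assumptions. A reader might infer that a body-weight link will be reported as an androgen link. The documents give no CNP-BMI, CNP-SHBG or BMI-androgen figure, and at 0.3 with both variables the rate at n = 36 is only 8%.
- BMI may be a mediator. If an androgen acts on CNP through BMI, the correlation pattern is the same as with BMI as a common cause, and the partial correlation removes a real total effect. These data cannot tell the two apart, so adjusted results should not replace the plain ones.

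It can also be said that the plan's wording would cover correlations of CNP with BMI and SHBG, so a reader might see the ambiguity. That helps only in part: seeing that CNP correlates with both BMI and an androgen does not show what remains once BMI is held constant.

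**Conclusion.** The concern holds in a conditional form. The androgen aim rests on two-variable correlations alone, nothing in design or analysis deals with body weight, and restriction to PCOS women would not cure this. The effect ranges from slight (8%) to severe (54%) at n = 36 as the assumed BMI correlations go from 0.3 to 0.6, and is larger if all 66 women are pooled.

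The built-in SHBG route concerns FAI only, and only under the assumed formula. A reader might extend it to the whole androgen aim. The documents do not support that, since total testosterone, androstenedione and DHEAS are listed separately and are affected only if they themselves correlate with SHBG. Nor do the documents support discounting any CNP-FAI correlation that lacks a matching testosterone correlation: FAI is meant to allow for binding, so SHBG is part of what it measures.

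This is a worthwhile, inexpensive improvement to a stated aim. It does not show that the planned test is invalid.

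**What to change.** 1. State that the androgen correlations are computed within the PCOS group. If pooled results are also wanted, label them as such.
2. For total testosterone, free testosterone, androstenedione, DHEAS and FAI, report a partial Spearman correlation with CNP controlling for BMI and age, beside the unadjusted rho.
3. Give the FAI formula. Show the CNP-total testosterone and CNP-SHBG correlations next to the CNP-FAI result. Do not adjust FAI for SHBG, which is its own component.
4. Describe a CNP-androgen link as independent of body weight only if the adjusted correlation supports it. Otherwise call it an unadjusted association.

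The cost is a few sentences, some extra runs on data already collected, and one or two degrees of freedom out of 34. If BMI lies on the causal path the adjusted rho can remove a real total effect, which is why both are shown. The plan is written in the past tense, so if the unadjusted results are already known, the adjusted ones should be marked as added afterwards.
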